By my signature, I confirm that my staff and I have carefully read and understand this protocol, protocol amendment, or amended protocol and agree to comply with the conduct and terms of the study specified herein and with any other study conduct procedures provided by Viking Therapeutics, Inc.

I agree to conduct the study according to this protocol and the obligations and requirements of clinical Investigators and all other applicable requirements listed on form 1572 and in 21 CFR part 50, 54, 56, and 312 and all applicable local, state, and federal regulations and ICH guidelines. I will not initiate this study without the approval of an Institutional Review Board (IRB).

I understand that, should the decision be made by Viking Therapeutics, Inc. to terminate prematurely or suspend the study at any time for whatever reason, such decision will be communicated to me in writing. Conversely, should I decide to withdraw from execution of the study, I will communicate immediately such decision in writing to Viking Therapeutics, Inc.

For protocol amendments, I agree not to implement the amendment without agreement from Viking Therapeutics, Inc. and prior submission to and written approval (where required) from the IRB, except when necessary to eliminate an immediate hazard to the subjects, or for administrative aspects of the study (where permitted by all applicable regulatory requirements).

Investigator's Signature

Date

Investigator's Name

Address:

**RETURN THE ORIGINAL SIGNED COPY TO INTEGRUM, LLC AND KEEP A XEROX
COPY IN THE REGULATORY BINDER AT YOUR SITE**

Synopsis

Title	A Phase II, Randomized, Double-Blind, Parallel Group, Placebo-Controlled, Multi-Center Study to Explore the Efficacy, Safety and Tolerability of VK5211 in Subjects with Acute Hip Fracture
Indication	Hip fracture
Clinical Phase	Phase IIa
Primary Objective	To determine the efficacy of VK5211 after 12 weeks of treatment based on mean placebo-corrected percentage change in total body less head (TBLH) lean body mass as assessed by whole body Dual Energy X-Ray Absorptiometry (DXA) scan.
Secondary and Exploratory Objectives	
Secondary
 
1) To assess the safety and tolerability of VK5211 after 12 weeks of treatment by comparing overall adverse events, vital signs, 12-lead ECG data, physical examinations, and hematology/chemistry/urinalysis data to placebo.2) To determine the efficacy of VK5211 after 12 weeks of treatment based on mean placebo-corrected change in:
• Hip bone mineral density (BMD) as assessed by DXA• Total lean body mass• Appendicular lean body mass• Bone turnover markers (s-CTX and s-PINP)3) To assess plasma concentration of VK5211 near T_{max} and at trough levels in relation to total lean body mass. 
Exploratory
 
To determine the efficacy of VK5211 compared to placebo after 12 weeks of treatment based on:
 
• Physical Performance Assessments
○ Six-Minute Walk Test (6MWT) and BORG Scale○ Grip Strength○ Short Physical Performance Battery (SPPB)• Patient Reported Outcomes
○ Physical activities of daily living (PADLs) and Instrumental activities of daily living (IADLs), pre- and post-fracture○ Short Form-36 (SF-36)
Study Design	
This is a randomized, double-blind, parallel group, placebo-controlled, multi-center study to investigate the safety, tolerability, and efficacy of VK5211 after 12 weeks of treatment.
 
Males and females ≥ 65 years old who are ambulatory and recovering from a hip fracture will be eligible for participation 3-11 weeks post-injury.
 
After completing all Screening requirements, subjects will be randomized to one of four treatment arms (VK5211 0.5 mg, 1.0 mg, 2.0 mg, or placebo) in a

	
1:1:1:1 ratio and will receive their first dose of study treatment in the clinic. Baseline procedures will include:
 
• Vital signs (systolic blood pressure, diastolic blood pressure, and heart rate)• Hematology/Chemistry/Urinalysis• Bone Turnover Markers• Vitamin D• Thyroid Markers• Fasting Lipid Profile• Coagulation• Pituitary/Adrenal Hormone Blood Tests• Pancreatic Endocrine Markers• DXA Scan• 12-Lead Electrocardiogram (ECG)• 6MWT and BORG Scale, Grip Strength, and SPPB• Post-fracture PADLs/IADLs• SF-36 
The first bottle of study treatment will be dispensed and subjects will be instructed to take one oral dose of the assigned treatment at approximately the same time every morning, 30 minutes prior to breakfast. They will receive a diary card to record their treatment administration and meal times for 3 days prior to Visit 2.
 
Within 1 week of randomization, subjects will receive a phone call to review concomitant medications, discuss adverse events, and review compliance.
 
Subjects will undergo safety and efficacy assessments as specified in the protocol on an approximately 4-week basis for a total treatment period of approximately 12 weeks. Following the 12-week treatment period, subjects will be followed for an additional 12-week period for assessment of safety and duration of drug effect.
 
During the study safety will be assessed on an ongoing basis by adverse events, identification of dose-limiting toxicities (DLTs) (if any), plasma concentrations, general physical examinations, vital signs, clinical laboratory assessments in blood, urine, as well as other specialized testing as required. Adverse events will be graded according to the Common Terminology Criteria for Adverse Events (CTCAE version 4.03 [http://evs.nci.nih.gov/ftp1/CTCAE/CTCAE_4.03_2010-06-14_QuickReference_8.5x11.pdf].

Total Sample Size	Approximately 120 subjects
Subject Selection Criteria	Recovering hip fracture patients ≥ 65 years old

More than 300,000 people in the U.S. experience hip fractures each year with the number expected to increase to 700,000 by 2050, driven by increased life expectancy and aging of the baby boom generation^{1,2}. Surgical intervention is the cornerstone of hip fracture treatment. The short-term goal of surgery is to stabilize the hip fracture and allow for weight bearing and movement in order to prevent sequelae from prolonged bed rest and allow for fracture healing.

Despite surgical intervention, recovery after hip fracture is often incomplete and is associated with high morbidity and mortality rates in the elderly. Mortality risks are at their peak in the first three months following hip fracture, with patients demonstrating a five- to eight-fold increased risk of dying during this period³. Many patients never regain complete pre-fracture mobility and require long term assistance, which has a negative impact on their quality of life⁴. Furthermore, refracture and rehospitalization rates remain high, contributing to the increased pressure on health system resources⁵.

The elderly population is often considered frail and undernourished^{6,7}, which may be due in part to an increased catabolic state⁸. An increased catabolic state leads to chronic muscle wasting and reduced muscle strength, often resulting in falls accompanied by impaired immunity and delayed wound healing. Since anabolic steroids have been shown to improve conditions associated with increased catabolic rates such as burns, chronic obstructive airway disease and acquired immune deficiency syndrome (AIDS), selective androgen receptor modulators (SARMS) could be similarly useful in hip fracture in the elderly⁹. SARMS may help to improve outcomes and recovery by promoting anabolic and bone strengthening activities, while at the same time avoiding the negative steroid side effects including changes in voice, growth of facial hair in women, hair loss, acne, thromboembolic events and liver damage.

1 ETHICS AND REGULATORY CONSIDERATIONS

1.1 Independent Institutional Review Board (IRB)

Before study initiation, the protocol and all amendments, consent form, subject recruitment materials and procedures (e.g., advertisements) and any other written information to be provided to subjects will be reviewed and approved by the relevant IRB.

The IRB will be provided with a copy of the Investigator Brochure information to be provided to subjects and any updates in accordance with local regulatory requirements. The IRB will be provided with reports, updates, and other information (e.g., Safety Updates, Amendments, and Administrative Letters) according to local regulatory requirements or Institution procedures.

1.2 Ethical Conduct of the Study

This document is a protocol for a human research study conducted according to US and international standards of Good Clinical Practice (FDA Title 21 part 312 and International Council for Harmonization guidelines), applicable government regulations and Institutional Research Policies and Procedures.

The study will be conducted as described in the approved protocol, with amendments. All revisions to the protocol will be discussed with, and will be prepared by the Sponsor, Viking Therapeutics. The Investigator will not have authority to implement any deviation or change to the protocol without prior review and documented approval/favorable opinion from the IRB of an Amendment, except where necessary to eliminate an immediate hazard to study subjects. Any significant deviation from the approved protocol will be documented in the Deviation Log.

Any deviation or change to the protocol required to eliminate an immediate hazard prior to obtaining IRB approval/favorable opinion, will be submitted as soon as possible to:

- IRB for review and approval/favorable opinion.
- Viking Therapeutics via appropriate designees.
- Regulatory Authorities, if required by local regulations.

Documentation of approval signed by the chairperson or designee of the IRB will be sent to Viking Therapeutics via appropriate designees.

If the revision is an Administrative Letter, Investigators will be required to inform their IRB.

If an Amendment substantially alters the study design or increases the potential risk to the subject: (1) the consent form will be revised and submitted to the IRB for review and approval/favorable opinion; (2) the revised form will be used to obtain consent from subjects currently enrolled in the study if they are affected by the Amendment; and (3) the new form will be used to obtain consent from any new subjects prior to enrollment.

1.3 Subject Information and Consent

The consent form will include all elements required by the International Council for Harmonization (ICH), good clinical practice (GCP) and applicable regulatory requirements and

adhered to GCP and to the ethical principles that have their origin in the Declaration of Helsinki. The consent form will also incorporate or include as an attachment an authorization to use or release individual health information for research. This authorization will include a statement that protected health information may be shared with Viking Therapeutics and/or its agents, other researchers participating in this research, and regulatory authorities. Prior to the beginning of the study, the Investigator will obtain the IRB's written approval/favorable opinion of the written informed consent form and any other information to be provided to study subjects.

The informed consent form and any other information provided to subjects or the subject's legally acceptable representative will be revised whenever important new information becomes available that was relevant to the subject's consent, and receive IRB approval/favorable opinion prior to use. The Investigator, or a person designated by the Investigator, will fully inform the subject or the subject's legally acceptable representative of all pertinent aspects of the study and of any new information relevant to the subject's willingness to continue participation in the study. This communication will be documented. Subjects will read and sign any and all revised informed consent forms.

During a subject's participation in the trial, any updates to the consent form and any updates to the written information will be provided to the subject.

2 INVESTIGATIONAL PLAN

2.1 Overall Study Design and Plan: Description

This is a randomized, double-blind, parallel group, placebo-controlled, multi-center study to investigate the safety, tolerability, and efficacy of VK5211 after 12 weeks of treatment.

2.2 Screening

Screening will take place 3-11 weeks post-injury. After signing the informed consent form, inclusion/exclusion criteria, concomitant medications, and medical history will be reviewed and demographic information will be collected. Subject will have a physical examination, including height and weight. Vital signs (systolic blood pressure, diastolic blood pressure, and heart rate) will be recorded. Samples will be collected for hematology/chemistry (with HbA1c)/urinalysis and prostate specific antigen (PSA, males only). A Mini Mental State Exam will be performed on all subjects to verify cognitive function. The 4-meter walk test will also be performed to verify ambulatory ability. A 12-lead ECG will be used to verify cardiac function. Pre-fracture physical and instrumental activities of daily living (PADLs/IADLs) will be conducted by subject interview. Baseline DXA scans will be scheduled at this time.

2.3 Randomization/Baseline

Approximately 1 week (± 2 days) after Screening (4-12 weeks post-injury), subjects will be expected to arrive at the clinic following a minimum 10-hour fast. They will be allowed to have a light snack after all bloodwork is complete.

Baseline procedures will include:

- Review concomitant medications
- Vital signs (systolic blood pressure, diastolic blood pressure, and heart rate)
- Hematology/Chemistry/Urinalysis
- Bone Turnover Markers
- Vitamin D
- Thyroid Markers
- Fasting Lipid Profile
- Coagulation
- Pituitary/Adrenal Hormone Blood Tests
- Pancreatic Endocrine Markers
- Dual-Energy X-Ray Absorptiometry (DXA) Scans
- 12-Lead ECG at 2 hours post-dose
- Six-Minute Walk Test (6MWT) and BORG Scale, Grip Strength, and Short Physical Performance Battery (SPPB)
- Post-fracture PADLs/IADLs
- Short Form-36 (SF-36)

Subjects will be randomized to one of four treatment arms (VK5211 0.5 mg, 1.0 mg, 2.0 mg, or placebo) in a 1:1:1:1 ratio and will receive their first dose of study treatment in the clinic. Adverse events will be recorded. A bottle of study treatment (30 capsules) will be dispensed and subjects will be instructed to take one oral dose of the assigned treatment at approximately the same time every morning, 30 minutes prior to breakfast. Subjects will be informed that they may have more doses than they will need and must return any extra study treatment at Visit 2. They will receive a diary card to record their treatment administration and meal and snack times for 3 days prior to Visit 2.

2.4 Visit 1: Telephone Contact

Within 1 week of randomization, subjects will receive a telephone call to review concomitant medications, adverse events, and compliance. Subjects will be reminded to take their assigned study treatment at approximately the same time every morning, 30 minutes prior to breakfast.

2.5 Visit 2

Approximately 4 weeks (no more than 30 days) after randomization, subjects will report to the clinic following a minimum 10-hour fast at approximately 8 am (Visit 2). A pre-dose blood sample will be drawn for the fasting lipid profile. A pre-dose plasma concentration blood sample will be drawn, the subject will be provided with one dose of their assigned treatment, and a post-dose plasma concentration blood sample will be drawn at 2 hours (± 10 min). They will have a physical examination, including weight, and vital signs will be recorded. Subjects will provide safety assessment samples for hematology/chemistry/urinalysis plus additional blood samples for bone turnover markers, pituitary/adrenal hormones, coagulation, and pancreatic endocrine markers. Following these blood tests, subjects will be allowed to have a light snack. They will provide data for Grip Strength, and SPPB. Post-fracture PADLs/IADLs will be conducted by subject interview. Following the interviews, they will perform the 6MWT and BORG Scale.

Concomitant medications, adverse events, compliance, and the diary card will be reviewed. The next bottle of study treatment (30 capsules) will be dispensed. Subjects will be reminded to take their assigned study treatment at approximately the same time every morning, 30 minutes prior to breakfast. Subjects will be informed that they may have more doses than they will need and must return any extra study treatment at Visit 3.

2.6 Visit 3

Approximately 8 weeks (no more than 60 days) after randomization, subjects will report to the clinic for Visit 3 and provide samples for plasma concentration, chemistry (GGT, ALT, AST, and total bilirubin), bone turnover markers and pancreatic endocrine markers. Vital signs will be measured. Subjects will provide data for Grip Strength, and SPPB. Post-fracture PADLs/IADLs will be conducted by subject interview. Following the interviews, they will perform the 6MWT and BORG Scale. Concomitant medications, adverse events, and compliance will be reviewed and the next bottle of study treatment (30 capsules) will be dispensed. Subjects will be informed that they may have more doses than they will need and must return any extra study treatment at Visit 4. They will receive a diary card to record their treatment administration and meal and snack times for 3 days prior to Visit 4. Subjects will be informed that they may have more doses than they will need and must return any extra study treatment at Visit 4. Visit 4 DXA scans should be scheduled at this time.

2.7 Visit 4

Approximately 12 weeks (no more than 90 days) after randomization, subjects will report to the clinic following a minimum 10-hour fast at approximately 8 am (Visit 4). A pre-dose blood sample will be drawn for the fasting lipid profile. A pre-dose plasma concentration blood sample will be drawn, the subject will be provided with one dose of their assigned treatment, and a post-dose plasma concentration blood sample will be drawn at 2 hours (± 10 min). Diary card data, concomitant medications, compliance, and adverse events will be reviewed. They will have a physical examination, including weight, and vital signs will be measured. They will provide safety assessment samples for hematology/chemistry/urinalysis and additional blood samples for bone turnover markers, serum calcium, vitamin D, thyroid markers, pituitary/adrenal hormones, PSA (males only), coagulation, and pancreatic endocrine markers. Following these blood tests, subjects will be allowed to have a light snack. Subjects will provide data for Grip Strength, and SPPB. Post-fracture PADLs/IADLs and SF-36 will be conducted by subject interview. Following the interviews, they will perform the 6MWT and BORG Scale. ECG and DXA scans will be performed. Visit 5 DXA scans should be scheduled at this time.

2.8 Visit 5

Approximately 24 weeks after randomization, subjects will report to the clinic following a minimum 10-hour fast for a follow-up visit (Visit 5) to provide a blood sample for plasma concentration, chemistry (GGT, ALT, AST, and total bilirubin), bone turnover markers, fasting lipid profile, and coagulation. Concomitant medications and adverse events will be reviewed. They will have a physical examination, including weight, and vital signs will be measured. They will provide data for the Grip Strength, and SPPB. Post-fracture PADLs/IADLs and SF-36 will

be conducted by subject interview. Following the interviews, they will perform the 6MWT and BORG Scale. ECG and DXA scans will be performed. Subjects will exit the study.

2.9 Early Termination

In case of early termination, the events will be performed according to [Table 1](#) and will be identical to Visit 4, excluding plasma concentration sample collection.

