4.3 Removal of Subjects from Therapy or Assessment

Subjects are free to withdraw consent and discontinue participation in the study at any time, without prejudice to further treatment. Subjects who discontinue prior to day 28 will be replaced.

A subject's participation in the study may be discontinued at any time at the discretion of the investigator. The following are reasons that may lead to a subject's discontinuation:

1. Subject develops intolerable adverse effects.
2. Subjects who experience a >60 msec prolongation of QTc interval or absolute QTc >500 msec (or >550 msec in the presence of a bundle branch block or paced ventricular rhythm) will be discontinued from treatment and followed by ECG until the QTc returns to baseline levels. Other abnormal findings on the ECG should be carefully considered and any subject excluded who, in the judgment of the PI, may not safely complete treatment in this study will be terminated from participation.
3. The subject is grossly non-compliant defined as:
 - a. Uncooperative/noncompliant and will not adhere to study responsibilities, including failure to appear at two consecutive visits.

- b. Taking prohibited medications as described in [Section 5.7.1](#), pending evaluation by the Sponsor.
- 4. The subject's health would be jeopardized by continued participation.
- 5. In the opinion of the Investigator, it is in the best interest to discontinue subject from study.
- 6. The subject wishes to withdraw for any reason.
- 7. The Sponsor elects to end the study, or any portion thereof, for any reason.
- 8. Any other safety results or adverse experiences that, in the opinion of the investigator, raise concerns about the safety or tolerability of VK5211.

Although a subject will not be obliged to give his/her reason for withdrawing prematurely, the Investigator will make a reasonable effort to obtain the reason while fully respecting the subject's rights. All subjects who are randomized and treated (i.e., received any amount of study drug) will be included in the safety analyses. Thus, every effort will be made to contact any subject who fails to attend any follow-up appointments/contacts, in order to ensure that he/she is in satisfactory health.

If a subject withdraws from the study as a result of meeting discontinuation criteria after the start of study drug administration, all post-treatment evaluations must be completed.

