6.10 DXA Scans

DXA scans will be performed at Randomization and at Visits 4 and 5, or in case of early withdrawal as shown in [Table 1](#). Instructions for DXA scans are provided in the study reference manual.

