7.7 Visit 4 (Day 84 -5/+2)

At Visit 4, the following will take place:

- Record concomitant medications
- Physical examination, including weight
- Vital signs (SBP, DBP, HR)
- Plasma concentration sample collection (pre-dose and 2 hours \pm 10 min post-dose)

- ECG at 2 hours post-dose
- Hematology/Chemistry/Urinalysis
- Thyroid Markers
- Vitamin D
- Bone Turnover Markers
- Pituitary/Adrenal Hormone Blood Tests
- Pancreatic Endocrine Markers
- Fasting Lipid Profile
- Coagulation
- PSA (males only)
- A light snack is permitted after bloodwork has been completed.
- DXA Scan
- Grip Strength and SPPB (to be performed before the PADLs/IADLs and SF-36)
- Post-fracture PADLs/IADLs
- SF-36
- 6MWT and BORG Scale(to be performed after the PADLs/IADLs and SF-36)
- Record adverse events
- Review diary card
- Review study treatment compliance and administer study treatment
- Schedule the Visit 5 DXA scan.

In case of early withdrawal, all Visit 4 events should be performed, excluding plasma drug concentration assessments and study drug dispensation.

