The subject must have a valid baseline DXA and a DXA after baseline and prior to 98 days after starting treatment.

For the lean body mass measurements, the number and percent of subjects who had a 0.5kg, 1.0kg, 1.5kg and 2.0kg increase from baseline will be presented, and the number and percent of subjects who increased by 3% and number and percent of subjects who increased by 5% will also be presented.

Correlations and regression lines between total lean body mass (for both observed values and change from baseline) and the VK5211 PK concentration near Tmax and at trough levels will also be analyzed for each VK5211 treatment group and all VK5211 treatment groups combined. This analysis will be performed by visit and for all post-baseline visits combined.

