2.14. Sample Size and Power Considerations

Power Considerations Prior to Study Start

Based on the observed change in total lean body mass information from previous studies (as percentage change in total lean body mass information is not available), it seems reasonable to estimate the placebo-adjusted difference in total lean body mass for the 0.5 mg group to be 0.5 kg and 1.0 kg for the 1 mg group. For the purpose of power calculations, the 2 mg group is extrapolated to show a 1.5 kg adjusted difference. The estimate of standard deviation, based on information from the previous study, is estimated to be 1.3. A sample size of 30 subjects per treatment group yields 84% power to detect a difference between the 1 mg treatment group and placebo and 99% power to detect a difference between the 2 mg treatment group and placebo.

Even though the sample size estimate is based on the observed change in total lean body mass, we believe that the resulting calculations are reasonable for the analysis of percentage change in body less head lean body mass.

120 subjects are required to have baseline and 3 months' post-treatment data to observe the power indicated above. The protocol was written to enroll 120 subjects, assuming that there would be no dropouts.

Power Considerations Once Approximately Half of the Subjects Completed Month 3

Once approximately half of the subjects had 3 month DXA data, the data was reviewed in a blinded fashion.

Modifications to the pre-study assumptions was considered appropriate.

A placebo adjusted change of 1.6, 2.4 and 4.1 for the 0.5 mg, 1.0 mg and 2.0 mg active groups respectively with a standard deviation estimate of 2.0 seemed to be more reasonable.

Under these assumptions, the power calculations are as follows:

- Placebo vs. 0.5 mg VK5211 – 26 subjects per treatment group yields 80% power
- Placebo vs. 1.0 mg VK5211 – 16 subjects per treatment group yields 90% power
- Placebo vs. 2.0 mg VK5211 – 7 subjects per treatment group yields 90% power

Based on these numbers, it seems reasonable to randomize 104 subjects to complete approximately 92 (approximately 23 subjects per treatment group to complete). Thus, the decision was made to stop enrollment prior to randomizing all 120 subjects.

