2.16. Handling Missing Data

Listings will be provided for all data. Descriptive statistics will be provided for all planned visits as provided on the Case Report Forms (CRFs).

Study days will be analyzed using the study days as reported in the Case Report Form. Likewise, unscheduled visits will not be reassigned a visit number based on the visit date.

Dates related to the adverse events and medications will be imputed using the rules below in an effort to categorize them properly into the summary tables.

Imputing partial or missing start dates:

- If the year is unknown, then the start date will not be imputed. The date will remain missing.
- If the month is unknown and the year is the same as the first dose date of the study, then impute the month and day of the date to be equal to the first dose month and day. Otherwise, impute the month as January.
- If the day is unknown and the month and year are the same as the first dose date of the study, then impute the day to be equal to the day of the first dose. Otherwise, impute the day as '01'.

Impute partial or missing stop dates:

- If the year is unknown, then the stop date will not be imputed. The date will remain missing.
- If the month is unknown, impute the month as December.
- If the day is unknown, impute the day to be the last day of the month.

If an imputed stop date is greater than the date of study completion/discontinuation date of the study, then the imputed stop date will be set equal to the date of completion/discontinuation date.

The imputed dates will be stored in the analysis datasets along with the original dates as recorded by the sites.

Efficacy and safety data collected at early termination visits will be included in the Month 3 and Month 6 analyses. Data collected on or prior to Day 112 (Day 84 + 28 Days) will be used for the Month 3 (Day 84) analyses. Data collected after Day 112 will be assigned to the Month 6 (Day 168) analyses.

For efficacy endpoints that have multiple post-baseline visits, last observation carried forward will be presented for the Month 3 and Month 6 visits. The DXA (both central reader and CRF), Six Minute Walk, Short Physical Performance Battery and SF-36 Scales will also have a multiple imputation method performed to address missing data as discussed in section 2.17.

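### Early Termination assessments taken well before 12 weeks can be analysed as Month 3, and the protocol does not clearly keep a willing subject who stops drug in the study for a Day 84 scan

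*Protocol*

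**What the plan says.** **Visit structure.** Protocol 2.9 states that the events at early termination "will be identical to Visit 4, excluding plasma concentration sample collection". Protocol 7.7 repeats this: "In case of early withdrawal, all Visit 4 events should be performed, excluding plasma drug concentration assessments and study drug dispensation". Protocol 6.10 has the same either/or form: "DXA scans will be performed at Randomization and at Visits 4 and 5, or in case of early withdrawal". In Table 1 the Early Term column has no study day. It carries the Study Disposition entry, which otherwise appears only at Visit 5, where Protocol 2.8 has subjects exit.

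**The conflicting line.** Protocol 4.3 ends by saying that, for a subject who withdraws as a result of "meeting discontinuation criteria after the start of study drug administration, all post-treatment evaluations must be completed". It does not list the evaluations or their timing. The same section says that subjects who discontinue before Day 28 are replaced.

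**Endpoint time.** The primary objective is change after 12 weeks. SAP 2.10.1 analyses it at Visit 4, for which the Table 1 window (Day 84, -5/+2) is Day 79 to Day 86.

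**Assignment to Month 3.** SAP 2.16 keeps what is gathered when a subject leaves early and sorts it by study day: "Data collected on or prior to Day 112 (Day 84 + 28 Days) will be used for the Month 3 (Day 84) analyses". Anything later goes to Month 6.

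**DXA filters.** SAP 2.10.2.1 gives two definitions of a valid scan for analysis. The stringent one needs at least 56 days on treatment and a scan within 14 days after stopping. The liberal one reads: "The subject must have a valid baseline DXA and a DXA after baseline and prior to 98 days after starting treatment". SAP 4.1 lists tables under both for the primary endpoint.

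**The concern.** A site following Table 1 can reasonably scan a subject on the day of stopping, record the disposition and close the subject out. The Day 84 value is then lost even if the subject would have come back for it.

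The early measurement stands in for it under the Month 3 label. A scan or walk test taken after a few weeks reflects neither 12 weeks of drug nor 12 weeks of further recovery. Time since fracture matters here: the protocol's introduction cites lean mass losses of up to 6% in the two months after injury. If stopping is more frequent or earlier in one arm, the arms are compared at different times.

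The SAP also holds three different limits for a Month 3 scan (Day 112, before 98 days, and 56 days on drug plus 14) and does not say which governs the primary result. That choice should be fixed before the data are unblinded.

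**Working it through.** **1. When an Early Termination value can count as Month 3**

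| Rule | Earliest | Latest |
|---|---|---|
| Planned Visit 4 (Table 1) | Day 79 | Day 86 |
| SAP 2.16 (all endpoints) | any day after baseline | Day 112 |
| Liberal DXA | any day after baseline | before 98 days |
| Stringent DXA | 56 days on treatment | 14 days after stopping |

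Under the stringent rule a scan can be 84 - 56 = 28 days early. Under the liberal rule it can be nearly 12 weeks early. 6MWT, SPPB and SF-36 have only the Day 112 limit.

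**2. Two example subjects**

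- *Stops on Day 40, scanned that day, willing to continue.* The liberal tables use the Day 40 scan as Month 3. The stringent tables drop the subject (40 < 56). Neither contains a Day 84 value, because no section plainly schedules one.
- *Completes drug and Visit 4 on Day 84, withdraws on Day 105.* The second DXA is 21 days after stopping (over 14) and past 98 days, so both definitions exclude it. The second 6MWT, SPPB and SF-36 fall before Day 112, so each has two Month 3 values and no rule prefers Visit 4. For DXA a duplicate needs withdrawal shortly after Visit 4: on Day 90, for instance, the second scan is 6 days after stopping and before 98 days.

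**3. The plan's own figures**

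The revised assumptions in SAP 2.14 are effects of 1.6, 2.4 and 4.1 with SD 2.0. I assume a two-sided 5% two-sample t-test, because the SAP states no alpha.

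- 26 per arm, effect 1.6: power 80.7% (stated 80%)
- 16 per arm, effect 2.4: 90.7% (stated 90%)
- 7 per arm, effect 4.1: 94.0% (stated 90%; 7 is the smallest number reaching it)

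SAP 2.14 also says "it seems reasonable to randomize 104 subjects to complete approximately 92". So 104 - 92 = 12 non-completers; 12/104 = 11.5%, or 3 of 26 per arm.

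**4. Illustration only**

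Suppose 3 of 26 per arm have an Early Termination scan on Day t counted as Month 3, the effect builds linearly to Day 84, and the SD is unchanged. None of this is in the documents. The effect is then multiplied by 1 - (3/26)(1 - t/84).

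- t = 28: multiplier 0.923. For 0.5 mg, 1.6 becomes 1.48 and power goes from 80.7% to 74.3%.
- t = 56: multiplier 0.962. For 0.5 mg, 1.6 becomes 1.54 and power is 77.6%.
- At t = 28, power is 97.5% for 1.0 mg and about 100% for 2.0 mg.

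The Day 28 case cannot arise in the stringent tables. There those subjects are absent: 23 per arm, and 75.6% power for 0.5 mg.

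The sign of the error depends on the question asked. For 2.0 mg, with scans at Day 28:

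- Early scans used as Month 3: 4.1 x (23 + 3 x 1/3)/26 = 4.1 x 24/26 = 3.78.
- Effect if all had stayed on drug: 4.1.
- Day 84 contrast if nothing is retained after stopping: 4.1 x 23/26 = 3.63.

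The early scan answers neither question.

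**The case against.** **The stringent definition already deals with it.** It removes subjects with under 56 days of drug, its tables come first in SAP 4.1, and the SAP attributes it to the protocol. This narrows the problem considerably. But the SAP does not name it primary, and Protocol 6.10, 9.2 and 9.3.1, where one would look, do not contain it. It still admits a scan 28 days early. It also selects on treatment duration after randomisation, in a population that SAP 2.2 says is analysed as randomised.

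**This is an on-treatment question in a Phase IIa dose-ranging study.** SAP 2.10.2.1 describes the Month 3 analysis that way, and it is a fair aim. It supports keeping the stringent analysis alongside. It does not support labelling a Day 40 scan as 12 weeks, nor forgoing the Day 84 scan.

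**Multiple imputation is planned.** It is, but SAP 2.17 bars it for values missing because of a treatment-related adverse event or lack of effect, where arms may well differ. It is also a poor substitute for a scan that could have been taken.

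**The protocol does not simply equate stopping drug with leaving.** Correct. The QTc item in 4.3 stops treatment and continues ECG follow-up, and the section's last line asks for later evaluations. A reader might infer from Table 1 that every subject who stops drug must exit. The documents conflict rather than settle it.

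**Subjects who stop before Day 28 are replaced.** So they are, but nothing says their Early Termination data are dropped.

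**Conclusion.** The point stands in limited form. The protocol does not plainly keep a willing subject who has stopped drug for a Day 84 DXA. SAP 2.16 and the liberal DXA definition let assessments taken weeks early count as Month 3. The primary DXA definition is not named. For the exploratory 6MWT, SPPB and SF-36 there is no rule for choosing between two Month 3 values.

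Three stronger readings are not supported:

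- A reader might infer that an early scan counts whenever it was taken. Values after Day 112 go to Month 6, and both DXA definitions set limits.
- A reader might take the Day 105 example as producing two Month 3 DXA scans. Both definitions exclude the second.
- A reader might treat the dilution figures as an estimate of bias. They assume that all 12 implied non-completers were scanned early on a common day and that the effect accrues linearly. SAP 2.14 does not say when or why subjects leave.

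The size is therefore unknown and probably modest: about 11.5% of subjects could be affected and, on the assumptions shown, 0.5 mg power falls by three to six points with little change at the higher doses. The change is worth making because it is cheap and because a lost Day 84 value cannot be recovered.

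**What to change.** **Protocol 4.3, 2.9, 7.7 and Table 1.** Reconcile these so that stopping study drug is distinct from leaving the study. Subjects who stop drug without withdrawing consent are asked to attend the Day 84 and Day 168 assessments already in Table 1, including DXA. The Early Termination visit is for those leaving the study. The criteria for stopping drug are unchanged.

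**SAP 2.16.** Use the Visit 4 value as Month 3 whenever it exists. Use an Early Termination value only when Visit 4 is missing and the value falls in a stated window, for example Day 84 +/- 14 days (Day 70 to Day 98). The upper end matches the liberal definition's 98-day limit; that limit is strictly before 98 days, so settle the edge day. Earlier values feed the planned multiple imputation and should not count as observed Month 3 data. The last-observation-carried-forward tables may still carry them, labelled as such.

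**SAP 2.10.2.1.** Name the primary DXA definition. The stringent analysis can be kept alongside as the on-treatment result.

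**Cost.** A short amendment and SAP wording, with no new type of visit or assessment. A few off-drug Day 84 values may slightly lower the estimated effect, and a few more Month 3 values will be imputed.
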